## 1 INTRODUCTION

The purpose of this statistical analysis plan (SAP) is to describe the procedures and the statistical methods that will be used to analyze and report efficacy and safety data for study A3309-012 based on protocol dated on 10 September 2019 (version 3.0).

### 1.1 STUDY OBJECTIVES

#### Primary Objective

- To evaluate the efficacy of repeated once-daily doses of 5 mg elobixibat on serum levels of low-density lipoprotein cholesterol (LDL-C) in patients with NAFLD or NASH.

#### Secondary Objectives

- To assess the safety and tolerability of elobixibat in patients with NAFLD or NASH
- To evaluate the effect of elobixibat on liver steatosis as measured by magnetic resonance imaging (MRI) for (i) liver fat fraction (using proton density fat fraction [PDFF]) and (ii) total liver fat (using whole liver fat volume)
- To evaluate the effect of elobixibat on liver function using alanine aminotransferase (ALT)
- To evaluate the effect of elobixibat on lipids and total bile acids in patients with NAFLD or NASH

### 1.2 STUDY ENDPOINTS

#### Primary Efficacy Endpoint

- Change from baseline in serum LDL-C at week 16.

#### Secondary Efficacy Endpoints

- Absolute change from baseline to week 16 in liver fat fraction (%) as measured by MRI-PDFF
- Absolute change from baseline to week 16 in total liver fat (mL) as measured by MRI
- Change from baseline to week 16, and follow-up in the following:
  - Serum ALT, AST, and gamma-glutamyl transferase
  - HDL-C, non-HDL-C, LDL-C/HDL-C ratio, and triglycerides
  - Total bile acids

#### Exploratory Efficacy Endpoints

- Change from baseline (unless otherwise specified) to week 4, week 8, week 12, week 16, and follow-up in the following:

- Fasting glucose, insulin, homeostatic model assessment-insulin resistance, HbA1c, free fatty acids
- GLP-1, FGF-19, and C4 levels
- High-sensitivity C-reactive protein (CRP)
- Lanosterol and beta-sitosterol
- Body weight, BMI, waist circumference, and waist-to-hip ratio
- Apolipoprotein A1 and Apolipoprotein B
- Fibrosis and inflammation markers: FIB-4, APRI, and NFS

## Safety Endpoints

The safety endpoints for this study include clinical laboratory assessments, vital signs, AEs, ECGs, and concomitant medications.

## 1.3 STUDY DESIGN

### General Study Design and Plan

This is a double-blind, randomized, placebo-controlled, Phase 2 study to explore the efficacy and safety of elobixibat (oral dose of 5 mg) once daily for 16 weeks in patients with NAFLD or NASH. The study includes a 6-week Screening Period, followed by a 16-week Treatment Period, and a follow-up visit 2 weeks after the last dose of study drug.

After completing the Screening period, eligible patients will be randomized on Day 1 (Visit 2) in a 1:1 fashion to either 5 mg/day elobixibat or matching placebo. There will be a total of 7 scheduled visits during the study, as follows:

- Visit 1: Screening period (week -6 through Day -1)
- Visit 2: Day 1/Randomization visit
- Visit 3: Week 4
- Visit 4: Week 8
- Visit 5: Week 12
- Visit 6: Week 16/End of Treatment (EOT). Any patient that discontinues treatment prematurely should complete this visit at the time of discontinuation
- Visit 7: Follow-Up period. The follow-up visit will occur 2 weeks after the last dose of study drug whether the patient completes the study or discontinues prematurely

Additional unscheduled visits may be required for patients who need direct site assistance (e.g., due to AE monitoring, in order to fulfill screening requirements, and/or for safety maintenance).

## **Randomization and Blinding**

A double-blind design is employed so that both the investigators and the patients will be unaware of the treatment assignment during the study. Eligible patients will be randomly assigned in a 1:1 ratio to the study drug or the matching placebo by the Interactive Web Response System (IWRS). Patients who withdraw from the study after the randomization visit are not to be replaced and their randomization number will not be reused.

To ensure blinding, the study drug and the matching placebo have the same shape and size. Labels on the treatment bottles will not identify the treatment to which a patient has been randomized. Traceability of the treatment is ensured by the bottle number. Other than designated randomization personnel, all study conduct persons, investigators, and patients are blinded to study drug assignment.

Per the protocol, total bile acids results are blinded. Operationally, blinding was implemented by not having total bile acids, FGF-19, C4, and lanosterol and beta-sitosterol results available until after database lock. The same blinding approach was applied to the imaging results for the post-baseline imaging results.

## **Sample Size**

Due to the exploratory nature of this study, no formal power calculations were used to determine the sample size. The number of subjects (46 patients in total, 23 patients per treatment group) was chosen based on clinical experience with other similar proof-of-concept studies.

## **2 STATISTICAL CONSIDERATIONS**

### **2.1 GENERAL CONSIDERATIONS**

General principles will be followed:

- Population summaries (e.g., disposition, demographics and baseline characteristics, medical/surgical history, prior and concomitant medications) and efficacy tables will summarize data by the randomized treatment group. Safety tables will be summarized by the actual treatment subject received.
- All continuous variables will be summarized using descriptive statistics including the number of patients with data to be summarized (n), mean, standard deviation (SD), median, minimum (min) and maximum (max). Minimum and maximum will be displayed with a maximum of 2 decimal places. Mean and median will be rounded to 1 additional decimal place, SD will be rounded to 2 additional decimal places, compared to the displayed minimum and maximum.
- Categorical variables will be summarized with count and percent; the denominator will be based on the number of subjects in the treatment group, unless otherwise stated.
- In general, efficacy analysis will be performed using the intent-to-treat (ITT) population and safety analyses will be performed using the safety population. Per-protocol population will be used for the primary endpoint sensitivity analysis.

- The default significance level will be (5%); confidence intervals (CIs) will be 95% and all tests will be two-sided, unless otherwise specified in the description of the analyses.
- P-values will be rounded to three decimal places. If a p-value is less than 0.001, it will be reported as “<0.001.” If a p-value is greater than 0.999 it will be reported as “>0.999”.

All analyses will be performed using SAS®, Version 9.4 or higher.

## 2.2 DEFINITIONS OF ANALYSIS SETS

### ITT Population

The intent-to-treat (ITT) population will include all patients who are randomized in the study and receive at least 1 dose of study drug. The ITT population will be used for all efficacy analyses based on the treatment randomized unless otherwise specified.

### Per Protocol Population

The per-protocol (PP) population will include all ITT patients who finish Visit 6/EOT with valid LDL-C measurements and do not have any important protocol deviations that may impact the analysis of efficacy. The important protocol deviations are:

- Failure to meet the Inclusion criteria
- Failure to meet the Exclusion criteria
- Compliance rate of <80% or >120% with study drug administration
- Took disallowed meds over 50% time of treatment period
- Others (mis-randomized, took the wrong drug, etc.)

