### 7.1.3.2.3 Study Week 16/Visit 6/EOT

The last dose of study drug will be taken in the morning the day before Visit 6 and the following procedures and assessments will be conducted (also conducted at the time a patient prematurely withdraws):

- 12-lead ECG (Section 10.2.6)
- Physical examination (Section 10.2.4)
- Vital signs (Section 10.2.5)
- Pregnancy test
- MRI (Section 9.2.2)

- Clinical safety laboratory tests (Section 10.2.1)
- Endocrinology (Section 10.2.1)
- GLP-1, FGF-19, C4 (Section 10.2.1)
- Total BA (Section 9.2.3)
- Lipid profile (Section 9.2.1)
- Fibrosis and inflammation markers (Section 10.2.1)
- High-sensitivity CRP
- Stored sample for future testing (Section 10.2.1)
- Review of concomitant medications
- AE monitoring

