## Analysis Visit

Visit-based data summaries will be presented by analysis visits. A window assessment will be performed according to the below table for any subject that missed a planned visit (on both efficacy and safety endpoints). The purpose of using this analysis window is to include potential unscheduled visits when a subject missed the planned visit. If a subject's planned visit assessment is out of the defined visit window and there is no unscheduled assessment within the same window, then this CRF collected planned visit assessment will be used for the analysis.

Period	Analysis Visit	Protocol Defined Window	Scheduled Study Day	Windows
Screening	Visit 1 (Screening)	-6 Weeks to Day -1	-41 to -1	<= -1
Treatment	Visit 2/ Randomization (Day 1)	Day 1	1	1
	Visit 3 (Week 4)	Week 4 ( $\pm 3$ days)	28	2, 42
	Visit 4 (Week 8)	Week 8 ( $\pm 3$ days)	56	43, 70
	Visit 5 (Week 12)	Week 12 ( $\pm 3$ days)	84	71, 98
	Visit 6/EOT (Week 16)	Week 16 ( $\pm 3$ days)	112	99, 119
Follow-up	Visit 7 (Follow-up)	Week 18 ( $\pm 3$ days)	126	$\geq 120$

If multiple records in the same analysis visit, the scheduled visit is preferred to the unscheduled visits, otherwise the one closest to the scheduled visit study day will be selected for the analysis and summaries. The later one is preferred if there are more than one record have the same distance to the scheduled study day.

In the derivation of post baseline extreme values (e.g., minimum, maximum, worst, last), all post baseline assessments will be included.

All data including additional unscheduled visits required for patients who need direct site assistance (due to AE monitoring, in order to fulfill screening requirements, and/or for safety maintenance) will be presented in subject listings unless otherwise specified.

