- **Step 2:** After the intermediate missing values have been imputed, subjects are categorized to 3 groups: 1) Completers (defined as subjects who completed the study treatment) in the control arm with non-missing value at week 16. 2) Subjects with a missing value at week 16 in both arms. Missing values in these subjects will be imputed using subjects in group 1. 3) Completers in the active arm with non-missing value at week 16 (based on the analysis visit window in section 2.3). These subjects will not be used to impute missing values in the next step.
- **Step 3:** At this point, each subject in the 200 data sets generated at step 1 either has complete data or has monotone missing data. Subjects in group 1 in Step 2 will be used to impute missing values in subjects in group 2. Missing data in group 2 will be imputed as the predicted value from a regression model with treatment arm, LDL-C baseline, baseline **lipid lowering medications**, and the change from baseline of all previous scheduled visits included in the model. Since the dataset has a monotone missing data pattern, the imputation process will start from the earliest visit with missing data (e.g. week 4) through week 16 in a sequential order. SAS Proc MI with option Monotone Reg, n impute=1, and seed = 25380 will be applied. The imputation will be done for each one of the 200 data sets generated at step 1.
- **Step 4:** After imputation for monotone missing values at Step 3, subjects in all 3 groups will be pooled and sorted by imputation sequence (variable name \_Imputation\_ from Step 1).
- **Step 5:** Each imputed complete dataset will be analyzed using the analysis of covariance (ANCOVA) model with the randomized treatment group as a factor and baseline LDL-C values

as a covariate. The estimates of least-square means (lsmeans), least-square mean differences 95% CI, and p-value will be generated for each one of the 200 imputed complete datasets.

- **Step 6:** The results from the 200 complete datasets, including lsmeans and lsmean difference with their corresponding 95% confidence intervals, and the p-value between elobixibat 5 mg and placebo will be combined using SAS® procedure PROC MIANALYZE for statistical inference.

The above primary efficacy analysis will be repeated using the PP population.

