### 3.3 STUDY DRUG EXPOSURE AND TREATMENT COMPLIANCE

Exposure will be analyzed by calculating the number of days with exposure to study drug. Descriptive summary statistics will be provided using the safety population.

The treatment compliance will be calculated as (the actual total dose / the expected total dose)  $\times 100$ , where:

- The actual total dose = (total number tablets of dispensed – total number of tablets returned)  $\times 5$  (Note: If tablets were not returned, the data will be considered missing.)
- The expected total dose = (last dose date – first dose date +1)  $\times 5$

The number of patients with an overall study treatment compliance <80%, between 80% and 120%, and >120% will be presented based on the safety population.

Treatment compliance for below time periods will be calculated and presented as the same categories as overall compliance:

- Day 1 to Week 4 [study day 1 to study day 28]
- Week 4 to Week 8 [study day 29 to study day 56]
- Week 8 to Week 12 [study day 57 to study day 84]
- Week 12 to Week16 [study day 85 to study day 112]

A subject level listing for study drug exposure (the first dose date, last dose date, duration of treatment) and compliance (including overall compliance and compliance by each time period defined above) will be presented.

Study drug dispensing and accountability will be listed as well.

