## **4 MINIMIZING RISK TO TRIAL INTEGRITY DURING THE COVID-19 PANDEMIC**

Missed or delayed study visits as a result of the COVID-19 pandemic have occurred. A listing of missed study visits and procedures will be provided. Should the MRI not occur on schedule, that is at the last visit on treatment, the validity of the liver fat quantification (measured by MRI PDFF) results may be compromised, as the potential effects of study drug on liver fat are expected to decrease once study treatment is stopped, although the speed of this loss of potential response is unknown. This loss of documented benefit may also be seen with other efficacy-based laboratory tests. For this reason, these endpoints may be tested in the per protocol population, in addition to the ITT population.

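### The listed per-protocol criteria exclude neither an adherent early discontinuer nor a scan taken after dosing has ended, although SAP Section 4 offers the PP set for late scans

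*SAP*

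**What the plan says.** SAP 2.2 defines the set by one visit and one analyte: "The per-protocol (PP) population will include all ITT patients who finish Visit 6/EOT with valid LDL-C measurements". The listed exclusions are eligibility failures, compliance below 80% or above 120%, prolonged use of disallowed medication, and an open-ended last item for other cases. Neither early discontinuation nor the timing of any assessment is listed.

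Four other provisions determine what this means in practice:

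- On Visit 6/EOT, SAP 1.3 says: "Any patient that discontinues treatment prematurely should complete this visit at the time of discontinuation".
- In SAP 3.3 the overall compliance denominator stops at the actual last dose. It begins "The expected total dose = (last dose date" and subtracts the first dose date.
- In SAP 2.3, if a planned visit falls outside its window and no unscheduled assessment lies inside it, "then this CRF collected planned visit assessment will be used for the analysis".
- SAP 3.2 ends the multiple-imputation procedure with: "The above primary efficacy analysis will be repeated using the PP population".

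On delayed visits, SAP Section 4 reports: "Missed or delayed study visits as a result of the COVID-19 pandemic have occurred". It explains that a scan not done at the last on-treatment visit may be compromised, because any effect on liver fat may be lost once treatment stops. It concludes: "For this reason, these endpoints may be tested in the per protocol population, in addition to the ITT population".

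**The concern.** A per-protocol analysis is read as an estimate in patients who took the treatment as planned and were measured as planned. The listed criteria do not secure either property, for two separate reasons.

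First, Visit 6/EOT is reached by stopping as well as by completing, and compliance is scored only over the days before stopping. A short course can therefore pass as full adherence. This is a problem of short exposure, not of an effect fading off drug.

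Second, Section 4 turns to PP because of late scans, but PP membership depends on LDL-C and says nothing about when the MRI was done.

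What is at stake is the interpretation of the PP results. If the affected patients remain in PP, agreement between PP and ITT does not show that the result is robust to early stopping or to late scanning.

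**Working it through.** The plan gives no figure to reproduce: the sample size of 46 has no power calculation, and no PP size is projected. The check applies the SAP's own rules to example patients.

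**1. Compliance of an early discontinuer.** Inputs: once-daily dosing for 16 weeks, so 16 × 7 = 112 planned tablets (Protocol 8.2), and PP limits of 80% to 120% (SAP 2.2). SAP 3.3 gives compliance = 100 × (tablets taken × 5) / ((last dose date − first dose date + 1) × 5). With every dose taken until stopping:

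| Last dose | SAP 3.3 overall rate | Share of the 112-day course |
|---|---|---|
| Day 28 | 28/28 = 100% | 28/112 = 25.0% |
| Day 56 | 56/56 = 100% | 56/112 = 50.0% |
| Day 84 | 84/84 = 100% | 84/112 = 75.0% |
| Day 89 | 89/89 = 100% | 89/112 = 79.5% |
| Day 90 | 90/90 = 100% | 90/112 = 80.4% |

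All five pass on the SAP formula. Changing only the denominator to the planned course would not be enough: the limit becomes 0.80 × 112 = 89.6 tablets, so the Day-89 stopper goes and the Day-90 stopper stays. If tablets are not returned, SAP 3.3 treats compliance as missing, and neither limit is triggered.

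**2. What that patient contributes to the PP repeat of the primary analysis.** There are two routes, and the SAP does not settle which applies.

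- Under the fallback in SAP 2.3, an LDL-C recorded as Visit 6 on Day 28 can serve as the Week 16 value.
- If Week 16 is instead treated as missing, SAP 3.2 imputes it from placebo completers.

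The grouping in Step 2 of SAP 3.2 has no place for an active-arm early discontinuer with an accepted Week 16 value, since its active group is restricted to completers. The sample code in the Appendix appears to place any active-arm patient with a Week 16 value alongside the completers. On neither route is the contribution a 16-week on-treatment value.

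**3. Late scan.** Protocol 7.1.3.2.3 says: "The last dose of study drug will be taken in the morning the day before Visit 6". Assume Visit 6 on Day 112, last dose on Day 111, LDL-C on time, and the MRI done later but recorded as Visit 6. Days off drug at the scan = scan day − 111:

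- Day 112: 112 − 111 = 1 day (on schedule)
- Day 126: 126 − 111 = 15 days
- Day 140: 140 − 111 = 29 days

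Compliance is 111/111 = 100% in each case, because scan date does not enter the formula. All three satisfy the listed PP criteria. The Visit 6 recording matters: an unscheduled record from Day 120 on would be assigned to Follow-up under SAP 2.3.

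**4. Influence of one patient.** Suppose one of n active-arm patients carries a share f of the full effect (0 ≤ f ≤ 1) and the others carry all of it. The arm's mean effect is then ((n − 1) + f)/n = 1 − (1 − f)/n, a dilution of (1 − f)/n.

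- n = 23: from 0 (f = 1) to 1/23 = 4.3% (f = 0)
- n = 18, an assumed PP size: from 0 to 1/18 = 5.6%

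**The case against.** The strongest reply concerns the primary endpoint. The multiple-imputation text seems to expect early terminators to have no Week 16 value, and the stated purpose of the SAP 2.3 windows is to pick up unscheduled visits when a planned one was missed. A valid LDL-C at Visit 6/EOT could be read as a valid Week 16 value, although the SAP does not define valid. This stands in part. A reader might infer that PP necessarily carries the short-exposure LDL-C values; the documents do not support that, because placebo-based imputation may replace them. It does not rescue the PP set, since the patient still enters it.

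On MRI, a reader might infer that every delayed visit produced an off-drug scan. That is not established either. The last dose is tied to Visit 6, not to Day 111, so dosing may have continued when the whole visit slipped; four bottles of 34 tablets (Protocol 8.1 and 8.2) give 136. Section 4 does not report on-time LDL-C with a late scan. The problem arises only where dosing ended before a delayed scan.

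Other provisions could exclude these patients. Protocol 8.5 divides by the amount that should be taken, which could mean the planned course, and SAP 3.3 also computes rates by four-week period; SAP 2.2 does not say which rate applies. The open-ended deviation item, the medical monitor's review (SAP 3.1), the noting of COVID-related violations (SAP 2.5) and allocation before unblinding (Protocol 11.2.1) allow case-by-case exclusion. That is a recognisable design, but none of it sets a rule on early stopping or scan timing. Protocol 11.2.1 names Visit 7/EOT instead of Visit 6/EOT, which does not help, since early discontinuers attend Visit 7 as well.

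Finally, the trial is exploratory, the PP analysis of MRI is optional, and the number affected is unknown. This is accepted and limits the size of the point.

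**Conclusion.** The point holds as a gap in the PP definition. On the listed criteria, an adherent Day-28 stopper is 100% compliant with 25% of the course taken, and a patient scanned after dosing has ended remains in the PP MRI analysis. Unless review or a different compliance reading removes such patients, PP cannot serve as a check against short exposure or, as Section 4 intends, against late scans.

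The size is modest: 0 to 4.3% dilution of the PP difference per affected active-arm patient with 23 per arm, or up to 5.6% with an assumed 18. These figures rest on a simple difference in means and on an assumed f; the scan dates in the example are also assumed.

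A reader might go further and conclude that the primary result is compromised. The documents do not support this. The ITT primary analysis, and MMRM run on the ITT set, do not use the PP definition. Only what the PP sensitivity analyses can show is affected. Amending the SAP is advisable, with medium confidence.

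**What to change.** Amend the SAP before unblinding; if unblinding has already occurred, label the change post hoc.

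- **PP membership (SAP 2.2).** Require completion of the 16-week treatment period and an observed Week 16 LDL-C within Days 99-119, without the out-of-window fallback. State which compliance rate applies. A planned-course denominator may be added but does not replace the completion rule.
- **Consistency (SAP 2.3 and 3.2).** Reconcile the fallback with Step 2 of the imputation, so that it is clear whether an early EOT LDL-C counts as Week 16 or as missing.
- **MRI (SAP Section 4).** For the PP analyses of MRI-PDFF and total liver fat, exclude scans taken more than a fixed number of days after the last dose. Set the number blind to treatment and to post-baseline imaging results, which SAP 1.3 says are withheld until after database lock. Repeat with a second cut-off, because Section 4 concedes that the rate of loss is not known.
- **Other endpoints.** Set any similar cut-off blind to treatment assignment. Blinding to results cannot be assumed for LDL-C or ALT, since SAP 1.3 does not list them among the withheld results.

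The cost is SAP wording and one derived variable, days from last dose to assessment; the last dose date is already in the planned listing (SAP 3.3). The downside is slightly fewer PP patients and some selection on a post-randomisation event. ITT remains primary.
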